10. Known history of hypotension or systolic blood pressure <85 mmHg at the Screening or baseline (Day 1) visit.
11. Diastolic blood pressure >90 mmHg at the Screening or baseline (Day 1) visit.
12. Known uncontrolled disorder of coagulation.  
Note: In the setting of well-controlled atrial fibrillation, prophylaxis for cardiovascular thromboembolism, or stroke with the following medications are allowed (aspirin, clopidogrel, prasugrel, dipyridamole, dabigatran, apixaban, rivaroxaban, or warfarin).
13. Chronic administration (defined as more than 14 continuous days) of immunosuppressants or other immune-modifying drugs within 6 months prior to the administration of the study injection. An immunosuppressant dose of glucocorticoid will be defined as a systemic dose  $\geq 10$  mg of prednisone per day or equivalent. The use of topical, inhaled, and nasal glucocorticoids will be permitted.
14. Participant has received or plans to receive any vaccine authorized or approved by a local health agency  $\leq 28$  days prior to study injections (Day 1) or plans to receive a vaccine authorized or approved by a local health agency within 28 days after the study injections.
15. Prior participation in research involving receipt of any IP (drug/biologic/device including any investigational RSV product) within 45 days before the planned date of the Day 1 study injection.
16. Participant has received a seasonal influenza vaccine or any other investigational influenza vaccine  $\leq 180$  days prior to the Randomization Visit.
17. Participant has tested positive for influenza by local health authority approved testing methods  $\leq 180$  days prior to the Screening Visit.
18. Participant had significant exposure to someone with severe acute respiratory syndrome coronavirus 2 (SARS-CoV-2) infection or COVID-19 in the past 10 days, as defined by the US Centers for Disease Control and Prevention (CDC) as a close contact of someone who has had COVID19.

19. History of a serious reaction to any prior vaccination, or Guillain-Barré syndrome within 6 weeks of any prior influenza immunization.
20. Receipt of systemic immunoglobulins or blood products  $\leq 90$  days prior to the Screening Visit or plans to receive systemic immunoglobulins or blood products during the study.

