#### **2.5.5.3. Concomitant Medications and Vaccines That May Lead to the Elimination of a Participant from the Per-Protocol Analyses**

The use of the following concomitant medications and/or vaccines will not require withdrawal of the participant from the study but may determine a participant's evaluability in the per-protocol (PP) analysis (analysis sets are described in [Section 2.8.4](#)):

- Any investigational or nonregistered product (drug or vaccine) other than the IPs used during the study period.
- A nonstudy vaccine (including authorized or approved vaccines for the prevention of COVID-19 regardless of the type of vaccine) administered during the period from 28 days before through 28 days after the study injection.
- Immunoglobulins and/or any blood products administered during the study period (except for treatment of COVID-19).

- Medications that suppress the immune system (except for treatment of COVID-19).

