#### **An IRT error**

On 07-March-2023, the Sponsor was informed of an error in the randomization ratio in Part A. The IRT vendor inadvertently inactivated the enrollment for Group 1 when 959 participants were randomized in Part A as part of a system build to fix an unrelated issue on 25-May-2022. Group 1 remained inactive until 25-Jul-2022 while the enrollment of Part A was completed on 09- June-2022. As a result, approximately 250 participants, instead of protocol planned 420 participants, were randomized in Group 1. This IRT error caused an under enrollment of around 170 participants in Group 1 and an over enrollment in Group 2 and 3; and the actual ratio for participants randomized in the three Groups was approximately 5:14:14.

The above information was received after the EDC database of Part A was locked but before the selected Sponsor and CRO personal, as defined by the study Data Blinding Plan, are to be unblinded to perform the analyses, and before the immunogenicity data become available. The assessment of actual randomization ratio was also conducted in a blinded fashion.

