### **2.4.3. Per-protocol Set**

#### **PP Set**

The PP Set consists of all participants in the FAS who receive the assigned study injections according to protocol, comply with immunogenicity blood sampling to have a baseline and at least one Day 29 post-injection assessment within the visit window of study day [22, 43], and have no major protocol deviations that impact the immune response.

The PP Set will be the primary population used for the analysis of immunogenicity data, and Participants will be included in the vaccination group to which they are randomly assigned.

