## 2.5.4. Immunogenicity Analysis

The analyses of immunogenicity will be using the PP Set, by vaccination group. The supportive analyses of immunogenicity especially for primary immune response will be conducted using the FAS based on [Appendix I](#). If the number of participants in the FAS and PP Set differ (defined as the difference divided by the total number of participants in the PP Set) by more than 10%, additional supportive analyses of non-primary immunogenicity may be conducted using the FAS.

The GMT, GMC, and GM level will be calculated using the following formula:

$$10^{\left\{ \frac{1}{n} \sum_{i=1}^n \log_{10}(y_{it}) \right\}}$$

where  $y_{1t}, y_{2t}, \dots, y_{nt}$  are  $n$  observed immunogenicity titers or levels for participants  $i=1, 2, \dots, n$  at time point  $t$ .

The GMFR measures the changes in immunogenicity titers or levels from baseline within participants. The GMFR will be calculated using the following formula:

$$10^{\left\{ \frac{1}{n} \sum_{i=1}^n \log_{10}\left(\frac{y_{it}}{y_{i0}}\right) \right\}} = 10^{\left\{ \frac{1}{n} \sum_{i=1}^n [\log_{10}(y_{it}) - \log_{10}(y_{i0})] \right\}}$$

where  $y_{1t}, y_{2t}, \dots, y_{nt}$  are observed immunogenicity titers or levels for participants  $i$ 's at time point  $t$ . and  $y_{10}, y_{20}, \dots, y_{n0}$  are immunogenicity titers or levels for participants  $i$ 's at time point 0 (baseline).

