#### **2.5.4.4. Analysis of Other Secondary Immunogenicity Endpoints**

The secondary immunogenicity endpoints include the following:

- GMT and GMFR of post-injection/baseline titers to RSV-A nAbs up to Day 181/EoS
- GMT and GMFR of post-injection/baseline titers to RSV-B nAbs up to Day 181/EoS
- SRR and proportion of participants with  $\geq$  2-fold increases in RSV-A nAb titers up to Day 181/EoS
- SRR and proportion of participants with  $\geq$  2-fold increases in RSV-B nAb titers up to Day 181/EoS.
- SCR and proportion of participants with  $\geq$  2-fold increases in influenza anti-HA Abs for each influenza strain at Day 181/EoS
- GMT and GMFR of influenza anti-HA Abs for each influenza strain up to Day 181/EoS

The statistical analyses are:

- GMT of RSV-A nAbs, RSV-B nAbs, and influenza anti-HA Abs for each influenza strain with corresponding 95% CI will be provided at Baseline (Day 1), Day 29, and Day 181/EoS by vaccination group. The 95% CIs will be calculated based on the t-distribution of the log-transformed values and then back transformed to the original scale for presentation. The following descriptive statistics will also be provided at Baseline (Day 1), Day 29, and Day 181/EoS: the number of participants (n), median, minimum and maximum. GMT with 95% CI will be plotted at Baseline (Day 1) and Day 29 by vaccination group.
- GMFR of RSV-A nAbs, RSV-B nAbs, and influenza anti-HA Abs for each influenza strain with corresponding 95% CI will be provided at Day 29 and Day 181/EoS over pre-injection at Day 1 [baseline] by vaccination group. The 95% CIs will be calculated based on the t-distribution of the difference in the log-transformed values (post-baseline time point – Day 1) and then back transformed to the original scale for presentation. GMFR with 95% CI will be plotted at Day 29 by vaccination group.

- Proportion of participants with  $\geq$  2-fold increases from Day 1 (baseline) in RSV-A nAb titers, RSV-B nAb titers, and influenza anti-HA Abs for each influenza strain at Day 29 and Day 181/EoS will be provided with 2-sided 95% CIs using the Clopper-Pearson method by vaccination group.
- SRR in RSV-A nAb titers and RSV-B nAb titers and SCR in influenza anti-HA Abs for each influenza strain at Day 181/EoS will be provided with 2-sided 95% CIs using the Clopper-Pearson method by vaccination group.

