## 7.9. Appendix I      Estimands and Estimand Specifications

**Table 8:      Intercurrent Events**

Label	Intercurrent Event Type
IcEv1 (early discontinuation or unrelated death)	Early discontinuation from study or unrelated death prior to Day 29, the first post-treatment immunogenicity result available.
IcEv2 (Alternative RSV vaccine, flu vaccine or SARS-CoV-2 vaccine)	Use of alternative RSV vaccine, flu vaccine or SARS-CoV-2 vaccine prior to Day 29.
IcEv3 (Prohibited medications)	Use of prohibited medications deemed to impact on immunogenicity prior to Day 29.

Abbreviation: IcEv: intercurrent event; RSV: respiratory syncytial virus.

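### Late HAI and SARS-CoV-2 antibody summaries keep samples taken after a licensed non-study influenza or COVID-19 vaccine, so the by-group levels are not the response to the study vaccine alone

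*SAP*

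**What the plan says.** **What is summarised.** In Part A, SAP 2.5.4.4 plans HAI GMT, GMFR, seroconversion rate and the proportion with at least a 2-fold rise at Day 181, by vaccination group. The GMFR sentence reads: "influenza anti-HA Abs for each influenza strain with corresponding 95% CI will be provided at Day 29 and Day 181/EoS". In Part B, SAP 3.5.4.4 plans the corresponding SARS-CoV-2 neutralizing antibody summaries at Days 57, 181 and 211. The stated secondary objectives (SAP 2.1.2.2 and 3.1.2.2) are the antibody responses to Afluria Quadrivalent and to mRNA-1273.214, with and without mRNA-1345.

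**In whom.** SAP 2.5.4: "The analyses of immunogenicity will be using the PP Set, by vaccination group". Besides a baseline sample, correct dosing and no major deviation affecting the immune response, the set requires "at least one Day 29 post-injection assessment within the visit window of study day [22, 43" (SAP 2.4.3; SAP 3.4 has the same window for Part B). It sets no condition at later visits.

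**Non-study vaccines.** Under Protocol 2.5.5.3, which Part B also uses, a non-study vaccine may affect per-protocol evaluability if "administered during the period from 28 days before through 28 days after the study injection". Exclusion criterion 14 in both parts bars someone who "plans to receive a vaccine authorized or approved by a local health agency within 28 days after the study injections" (Part B excepts SARS-CoV-2 vaccination as described in its inclusion criterion 2). The intercurrent event in SAP Appendix I, Table 8 is "Use of alternative RSV vaccine, flu vaccine or SARS-CoV-2 vaccine prior to Day 29".

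**What is recorded.** Non-study vaccinations are collected through end of study (Protocol 2.5.5.2 and 3.5.5.2). The SAP tabulates them within 7 and 28 days of injection; later ones appear only in a listing (SAP 2.5.2.4).

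**The concern.** A participant can receive a licensed influenza or COVID-19 vaccine between Day 29 and the last blood draw without breaching the protocol and without leaving the per-protocol set. The late titer then reflects the study vaccine plus the other vaccine, yet it is tabulated under the study vaccination group.

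At stake is the reading of persistence. A Day 181 HAI level, or a Day 181 or 211 SARS-CoV-2 level, would naturally be taken as what remains of the response to the study vaccine. With later vaccination mixed in, it is not that. The planned tables give no count by group of late vaccinations, so the reader cannot judge how much mixing occurred.

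The protocol itself treats such exposure as relevant. Part A excludes influenza vaccination within 180 days before randomization, and its sites record current-season influenza vaccine as a separate item.

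**Working it through.** The plan gives no figure on this point to reproduce. The check is a reading of the rules, then calendar arithmetic, then an illustration of why the effect cannot be sized.

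**1. Could any stated rule remove a late sample?**
- Per-protocol set: fixed by baseline, Day 29 and major deviations. It has no Day 181 or Day 211 condition.
- Licensed-vaccine rule (Protocol 2.5.5.3): ends 28 days after the study injection. The rule covering the whole study period is limited to investigational or nonregistered products.
- Table 8: stops at Day 29, and the immune estimands in Appendix I cover primary endpoints only.
- Visit windows (SAP Appendix B): map samples by nominal visit or study day, whatever has been given in between.
- Major deviations (SAP 2.5.2.7): to be determined by the sponsor, with no late-vaccine rule stated. Removing the participant from the set would also discard a valid Day 29 sample.
- SAP Section 5: silent on this.

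None does. With no other data imputed (SAP 2.5.1), the default is to use every observed sample.

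**2. Length of the uncovered period.** Day 1 is the day of injection, so 28 days later is Day 29.
- Part A, Days 30 to 181: 181 − 29 = 152 days.
- Part B, Days 30 to 211: 211 − 29 = 182 days. If the 28 days also run from the Day 29 injection, they end at Day 57, leaving 211 − 57 = 154 days. Day 57 is therefore arguable; Days 181 and 211 are not.

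**3. Part A calendar.** SAP 2.3.4 says Group 1 was inactivated "when 959 participants were randomized in Part A as part of a system build to fix an unrelated issue on 25-May-2022" and that "the enrollment of Part A was completed on 09- June-2022".
- Randomized after that point, if the total was about 1620 as planned: 1620 − 959 = 661, all in Groups 2 and 3.
- Check on Group 1: 959 × 7/27 = 249, against the stated approximate 250.
- Check on the ratio: (959 − 249 + 661)/2 ≈ 686 in each of Groups 2 and 3. This gives 249:686:686, or about 5:13.8:13.8, against the stated 5:14:14.
- Share of Groups 2 and 3: 1620 − 250 = 1370, and 661/1370 = 48%.
- Nominal Day 181 is Day 1 + 180 days: 25 May gives 21 November 2022, and 9 June gives 6 December 2022 (dosing taken as the day of randomization).

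The study vaccine carried the 2021-2022 strains (Protocol 1.1.2), and these visits fall in the following autumn and winter, so another season's vaccine could have come in between. Part B enrollment dates are not given, so no such calculation is possible there.

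**4. Why the effect cannot be sized.** Uptake *q* and fold rise *F* are not in the documents. The values below are assumptions for illustration.
- One group's GMT is multiplied by *F*^*q*: 1.5^0.1 = 1.04, 4^0.3 = 1.52, 4^0.5 = 2.00.
- Group ratio, *if* revaccination multiplies titers by the same fold in both groups: unchanged with equal uptake. With uptake 5 points apart it shifts by 1.5^0.05 = 1.02 to 4^0.05 = 1.07, or the reciprocal, depending on which group has more.
- Group ratio, *if* revaccinated participants instead reach the same titer in both groups: it moves toward 1 even with equal uptake. A true 0.667 would appear as 0.667^(1−*q*) = 0.695, 0.753 or 0.817 at *q* = 10%, 30% or 50%.

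The last two models disagree, and the documents do not favour either.

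**The case against.** The strongest reply is that nothing is undefined. The SAP summarises observed titers, so the analysis is treatment policy in all but name, and a programmer would know what to do. That stands, and it is why the point concerns interpretation and a missing supplementary analysis, not a hole in the specification.

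Second, the objectives are comparative, and participants remain blinded (SAP 2.3.5), so similar uptake across groups is plausible. That stands in part. Equal uptake protects the ratio only under a common fold rise, and the planned output is by-group levels, which equal uptake does not protect. A reader might infer that the comparison of coadministration with separate vaccination is biased. The documents do not support that: no between-group HAI or SARS-CoV-2 contrast is specified for these late visits in SAP 2.5.4.4 or 3.5.4.4, and neither size nor direction can be derived.

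Third, Group 1 received no study influenza vaccine, so its Day 181 HAI gives some view of background vaccination and infection. This is useful but imperfect, because Group 1 stopped enrolling on 25 May and its Day 181 visits fall earlier in the season.

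Fourth, excluding post-vaccination samples selects on a post-randomization event and leaves infection in. True; that version therefore belongs beside the all-observed one and should not replace it.

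**Conclusion.** The late summaries are specified in a way that keeps samples taken after a licensed non-study influenza or COVID-19 vaccine. Part A Day 181 HAI and Part B Day 181 and Day 211 SARS-CoV-2 levels therefore cannot be read as the response to the study vaccine alone. This rests on the text and needs no assumption. Part B Day 57 is arguable.

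The calendar figure, about 661 of about 1370 (48%), rests on the planned total of about 1620 and on dosing at randomization. A reader might take it as the number of contaminated samples. It is only the number whose nominal visit falls between 21 November and 6 December 2022; how many had another vaccine by then is not in the documents. Nor should the 120-day post-booster spacing at Part B entry be used to date later COVID-19 vaccination: it is an eligibility criterion, allows less per local guidance, and does not govern what happens after Day 1.

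The consequence is limited. These endpoints are descriptive and outside multiplicity control (SAP 2.5.5 and 3.5.5). The RSV summaries and every Day 29 co-primary and key secondary test are unaffected, and no decision rule changes. The change is still worth making because a stated secondary objective is affected and the remedy is cheap.

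**What to change.** In SAP 2.5.4.4 and 3.5.4.4, for HAI and SARS-CoV-2 neutralizing antibody after Day 29:

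1. Keep the all-observed summaries and label them as treatment policy with respect to non-study vaccination.
2. Add a supplementary version that excludes HAI samples from the date of a non-study influenza vaccine onward, and SARS-CoV-2 samples from the date of a non-study COVID-19 vaccine onward. Exclude the sample, not the participant, so that Day 29 data stay in.
3. Label that version as subject to post-randomization selection and as not removing infection.
4. Tabulate, by vaccination group, late non-study influenza and COVID-19 vaccination and the number of samples excluded.
5. Record in SAP Section 5 that the Part A rule was added after the EDC lock. SAP 2.3.4 places that lock before the 7 March 2023 notification of the IRT error.

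Leave Table 8, the RSV summaries and all Day 29 analyses as they are. The cost is a few sentences of SAP text, a second set of late HAI and SARS-CoV-2 tables, and one vaccination table. No new data are needed, since non-study vaccinations are already recorded through end of study, and no sample size changes. The supplementary version will have fewer participants; the all-observed version beside it lets the reader see whether that matters.

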#### **2.5.4.5. Analysis of Exploratory Immunogenicity Endpoints**

The exploratory immunogenicity endpoints include the following:

- GMC and GMFR of post-injection/baseline concentration to RSV bAbs up to Day 181/EoS
- Proportions of participants with  $\geq$  2-fold and  $\geq$  4-fold increases in RSV bAb concentration up to Day 181/EoS

The following analyses may be performed:

- The analyses of GMC and GMFR of RSV bAbs will be conducted in the same way as the analyses of GMT and GMFR described in [Section 2.5.4.4.](#)
- The analyses of proportions of participants with  $\geq$  2-fold and  $\geq$  4-fold increases in RSV bAb concentration will be conducted in the same way as the analyses of proportions described in [Section 2.5.4.4.](#)

Similar definition and analysis as SRR of RSV nAbs may also be applied on SRR of RSV bAbs.

#### **2.5.4.6. Subgroup Analysis**

All the above specified immunogenicity analyses may be performed by the following subgroup as applicable:

- Age groups: 50 to 59 years, 60 to 64 years,  $\geq$  75 years
- Age group (50 to 59 years,  $\geq$  60 years)
- Sex (male, female)

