The proportion of participants with at least 2-fold and at least 4-fold increases in titers/concentration (relative to baseline) will be provided by timepoint with the 2-sided 95% CI using the Clopper-Pearson method at Day 29. The number and percentage of participants with 2- and 4-fold increases will be provided with the 2-sided 95% CI using the Clopper-Pearson method. To compare the 2- and 4-fold increase rates between the vaccination groups, the Miettinen-Nurminen's method will be used to calculate the 95% CI for the difference in the fold-rise increase rates. The 2- and 4-fold rate difference, with the corresponding 95% CI at Day 29, will be provided.

Descriptive statistics (including 95% CIs) of the immunogenicity endpoints will also be provided by vaccination group and age group (50 to 59 years, 60 to 74 years, and  $\geq 75$  years).

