#### 4.8.5. Statistical Methods

##### 4.8.5.1. Immunogenicity Analysis

Unless otherwise specified immunogenicity analysis for Part C will be based on the Part C PP Set.

The primary immune endpoints based on RSV-A nAbs at BD Day 29 will be presented by descriptive summary statistics, such as median, minimum, maximum, and 95% CI for GMT. GMR will also be estimated to compare the immune response at BD Day 29 with the response at Day 29 post primary dose (ie, the primary  µg of mRNA-1345). GMR will be calculated by back transforming the mean of paired difference of RSV-A nAbs on the logarithmic scale between BD Day 29 and Day 29 post primary dose. The 95% CI for the GMR will be based on

t-distribution of the log-transformed values then back transformed to the original scale for presentation.

The primary immune endpoints that are based on RSV-B nAbs at BD Day 29 will be presented by the same methods as the methods for the primary immune endpoints of RSV-A nAbs at BD Day 29.

SRR of RSV-A nAbs or RSV-B nAbs is defined as proportion of participants with postinjection titers  $\geq 4 \times$  LLOQ if baseline is  $<$  LLOQ or a  $\geq 4$ -fold increase from baseline if baseline is  $\geq$  LLOQ. Baseline value is defined as the most recent nonmissing immune measurements collected before the mRNA-1345 primary dose. The difference and 95% CI of difference in the SRR at BD Day 29 versus the SRR at Day 29 post primary dose in the same participant will be estimated through a logistic model with repeated measure (via PROC GENMOD) in SAS.

GMT with 2-sided 95% CIs and GMFR with 2-sided 95% CIs at each postbaseline timepoint will be provided. The number and percentage of participants with seroresponse at each postbaseline timepoint will also be provided with 2-sided 95% CIs using the Clopper-Pearson method. The proportion of participants with at least a 2-fold increases in titers (relative to baseline) will also be provided at each postbaseline timepoint with the 2-sided 95% CI.

For summarizations of the GMT, GMFR, and GMR, the Ab titers reported as below the LLOQ will be replaced by  $0.5 \times$  LLOQ. Titers greater than the ULOQ will be replaced by ULOQ.

Descriptive statistics (including 95% CIs) for the immunogenicity endpoints may also be provided by initial vaccination group and/or by the age at enrollment (50 to 59 years, 60 to 74 years, and  $\geq 75$ ) in Part B.

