## 2.3. Study Design

### 2.3.1. Overall Study Design

Part A is a Phase 3, randomized, observer-blind study to evaluate safety, tolerability, and immunogenicity of mRNA-1345, an mRNA vaccine targeting RSV, when given alone or coadministered with a seasonal influenza vaccine (Afluria Quadrivalent) in adults  $\geq$  50 years of age.

All participants will participate in a Screening period (up to 14 days before Day 1), treatment period (vaccine and/or placebo administration on Day 1 [Baseline]), and a follow-up period (up to 6 months after vaccination). The SoA is provided in [Appendix F](#).

The study will enroll approximately 1620 medically stable adults  $\geq$  50 years of age. On Day 1, each participant will receive 2 injections administered IM, one in each arm, in the deltoid muscle. Participants will be randomized as shown in [Table 1](#) to receive either 1) mRNA-1345 (█ μg) + placebo (0.9% sodium chloride [normal saline]); 2) mRNA-1345 (█ μg) + Afluria Quadrivalent; or 3) Afluria Quadrivalent + placebo. Randomization will be stratified by age (50 to 59 years, 60 to 74 years, and  $\geq$  75 years). The study will target enrollment of approximately 20% of participants 50 to 59 years of age.

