### 2.5.2. Background Characteristics

#### 2.5.2.1. Participant Disposition

The number and percentage of participants in the following categories (analysis sets defined in [Section 2.4](#)) will be summarized by vaccination group as defined in [Section 2.5.1](#) based on Randomization Set:

- Randomization Set
- Full Analysis Set
- Per-protocol Set
- Safety Set
- Solicited Safety Set

The percentages will be based on the number of participants in the Randomization Set (as randomized), except that for the Safety Set and Solicited Safety Set in which the percentages will be based on the number of participants in the Safety Set (as treated).

The number of participants in the following categories will be summarized based on participants screened:

- Number of participants screened

- Number and percentage of screen failure participants and the reason for screen failure

The percentage of participants who screen failed will be based on the number of participants screened. The percentage of participants reporting each reason for screen failure will be based on the number of participants who screen failed.

The number and percentage of participants in each of the following disposition categories will be summarized by vaccination group based on the Randomization Set:

- Received any study injection
- Completed the study
- Prematurely discontinued the study and the reason for discontinuation

The number and percentage of participants by IRT randomized stratum (50 to 59 years, 60 to 74 years and  $\geq$  75 years) will be presented by vaccination group. Also, the concordance between IRT randomized stratum and CRF derived stratum will be tabulated by vaccination group.

A participant disposition listing will be provided, including informed consent, participants who completed the study injection schedule, participants who completed study, participants who discontinued from participation in the study, with reasons for discontinuation. A separate listing will be provided for screen failure participants with reasons for screen failure.

A participant, who has completed the last scheduled procedure on Day 181 (i.e., 6 months after administration of the study injections on Day 1), is considered to have completed the study.

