### **2.5.2.2. Demographics and Baseline Characteristics**

Descriptive statistics will be calculated for the following continuous demographic and baseline characteristics: age (years), weight (kg), height (cm), BMI ( $\text{kg}/\text{m}^2$ ). The number and percentage of participants will be provided for categorical variables such as randomized and actual age group (50 to 59 years, 60 to 74 years, and  $\geq$  75 years), gender and race. The summaries will be presented by vaccination group as defined in [Section 2.5.1](#). The summaries will be provided separately based on the Randomized Set, FAS, Safety Set, Solicited Safety Set, PP Set, and Supportive PP Set.

In the Supportive PP Set, participants will be presented by the vaccination group as Group 1 participants from mRAN-1345-P302, participants from mRNA-1345-P301, and Group 2 participants from mRNA-1345-P302. Group 1 participants from mRAN-1345-P302 and participants from mRNA-1345-P301 will also be pooled together as an “Adjusted Group 1” in the summary. The descriptive statistics for age (as a continuous variable), age group (50 to 59

years, 60 to 69 years, 70-79 years, and  $\geq$  80 years), weight, height, BMI, gender, and race will be presented by the vaccination group.

For screened failure participants, age (years), as well as gender, race, ethnicity will be presented in a listing.

In addition, participants with any inclusion and exclusion criteria violation will also be provided in a listing.

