#### **4.5.4.5. Subgroup Analysis**

All the above specified immunogenicity analyses may be performed by the following subgroup as applicable:

- Age groups at enrollment in Part B (50 to 59 years, 60 to 64 years,  $\geq$  75 years)
- Age groups at enrollment in Part B (50 to 59 years,  $\geq$  60 years)
- Sex (male, female)
- Race (White, Black, Asian, Other [including American Indian or Alaska Native, Native Hawaiian or other Pacific Islander and other races]))
- Ethnicity (Hispanic or Latino, Non-Hispanic or Latino)

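### The SAP's three-level age grouping for immunogenicity prints 60 to 64 where every other three-level age split uses 60 to 74, leaving ages 65 to 74 without a category

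*SAP*

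**What the plan says.** SAP 2.5.4.6 introduces the Part A immunogenicity subgroups with "All the above specified immunogenicity analyses may be performed by the following subgroup as applicable". The first grouping listed is "Age groups: 50 to 59 years, 60 to 64 years", followed by 75 years and over. A two-level split (50 to 59, 60 and over) and sex follow. SAP 3.5.4.6 repeats these age bands for Part B. SAP 4.5.4.5 does the same for Part C: "Age groups at enrollment in Part B (50 to 59 years, 60 to 64 years", again followed by 75 and over.

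Elsewhere the middle band is 60 to 74:

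- **Randomisation (SAP 2.3.1; likewise 2.3.4 and 3.3.1):** "Randomization will be stratified by age (50 to 59 years, 60 to 74 years, and" 75 and over.
- **Disposition (SAP 2.5.2.1):** "IRT randomized stratum (50 to 59 years, 60 to 74 years and" 75 and over.
- **Main demographics (SAP 2.5.2.2):** "randomized and actual age group (50 to 59 years, 60 to 74 years, and" 75 and over.
- **Safety subgroups (SAP 2.5.3.1 and 2.5.3.2.7):** the same three bands.
- **Protocol 2.8.5.1 (Part A) and 3.8.1.1 (Part B):** descriptive immunogenicity statistics "will also be provided by vaccination group and age group (50 to 59 years, 60 to 74 years, and" 75 and over.
- **Protocol 4.8.5.1 (Part C):** such statistics "may also be provided by initial vaccination group and/or by the age at enrollment (50 to 59 years, 60 to 74 years" and 75 and over.

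**The concern.** A three-level age grouping should place every participant in one band. As printed, someone aged 65 to 74 belongs to none. The list governs all the immunogenicity analyses specified before it, so age breakdowns of the co-primary and key secondary endpoints are included.

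A programmer following the SAP would produce three-level tables without that age range. Comparing the three Parts' subgroup sections would not expose the error, because all three carry it. The tables would not supply the 60 to 74 summaries described in the protocol, and their middle band could not be set beside the middle band of the safety tables. The 50 to 59 and 75-and-over bands would remain comparable, as would the two-level split.

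**Working it through.** No power, sample size or alpha figure is at issue. The check is of age coverage and of consistency between sections.

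**Coverage, ages 50 upward**

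| Grouping | Bands | Ages unassigned |
|---|---|---|
| As printed (SAP 2.5.4.6, 3.5.4.6, 4.5.4.5) | 50–59, 60–64, ≥75 | 65 to 74: 74 − 65 + 1 = 10 single years |
| Randomisation strata | 50–59, 60–74, ≥75 | none |
| Two-level split in the same three sections | 50–59, ≥60 | none |

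Replacing 64 by 74 closes the gap and reproduces the strata exactly.

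**Consistency**

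- 60 to 64 is printed in 3 places: SAP 2.5.4.6, 3.5.4.6 and 4.5.4.5.
- 60 to 74 is printed in 7 places in the SAP: 2.3.1, 2.3.4, 2.5.2.1, 2.5.2.2, 2.5.3.1, 2.5.3.2.7 and 3.3.1.
- 60 to 74 is printed in 7 places in the protocol: the Part A and Part B synopses (2.1.1, 3.1.1), the general designs (2.3.1, 3.3.1) and the immunogenicity analysis sections (2.8.5.1, 3.8.1.1, 4.8.5.1).
- The count is 7 + 7 = 14 against 3.

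SAP 2.5.2.2 also uses 60–69, 70–79 and 80 and over, but only for the Supportive PP Set. That grouping has no gap and gives no support to a 60–64 band.

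**Slip or intention**

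A deliberate 60–64 band would need a 65–74 band beside it, and there is none. SAP section 5 lists four changes from the protocol, none of which concerns age.

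**How many participants**

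The only relevant figures are the enrolment targets for ages 50 to 59, which are 20% in Part A and 35% in Part B:

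- Part A, 60 or over: (1 − 0.20) × 1620 = 1296
- Part B, 60 or over: (1 − 0.35) × 1680 = 1092

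These are loose upper bounds on the number omitted. They include ages 60–64 and 75 and over, which the misprint keeps, and they count planned enrolment where the analyses use the PP Set. No corresponding target is given for Part C.

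**Effect on the tests**

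The hierarchies in SAP 2.5.5 and 3.5.5 and the success rule in 4.5.5 contain no subgroup. The ANCOVA models in 2.5.4.2.1 and 3.5.4.2.1 adjust for randomised age group, where the middle band is 60 to 74. The Part C primary analysis is a paired comparison with no age term.

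**The case against.** The best opposing case accepts the misprint and disputes its weight.

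- **The outputs are optional and descriptive.** This stands. The safety subgroup tables are also only optional, so the lost comparison is between two sets of tables that may never be produced.
- **Ages 65 to 74 are still covered by the two-level split.** This stands, but that split cannot show them separately from those aged 75 and over.
- **The precedence rule does not settle the matter.** SAP section 1 puts the SAP above the protocol where methods differ, but much of this conflict lies within the SAP, where the rule is silent. That is fair. It remains true that no text resolves the conflict in favour of 60 to 74, and that a literal reading of the rule favours the misprint over the protocol's age summaries.
- **The protocol's commitment was already weakened.** For Parts A and B the protocol says the age summaries will be given, while the SAP says they may be. Correcting the band does not restore the commitment. This stands as a separate point.
- **Silence in SAP section 5 is weak evidence.** That list is not exhaustive: the SAP's narrower PP Set, which requires a Day 29 sample within study days 22 to 43, is not on it either. The gap itself is the stronger evidence of a slip.
- **The database lock does not show that tables were run.** SAP 2.3.4 says the randomisation error became known after the Part A database lock but before unblinding and before immunogenicity data were available. This stands; whether any table has used the 60–64 band is unknown.

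None of these points makes the printed grouping correct.

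**Conclusion.** The point holds. One band of one optional three-level grouping is wrong in three SAP sections, covering all three Parts, and ten single years of age are left out. Reading it as a slip rests on the gap and on the 14-to-3 count; no document states the intention. The noninferiority tests and the two-level age tables are unaffected. The number of participants who would be omitted cannot be derived from the documents. The correction should be made because the text is an operative instruction and would produce incomplete tables if followed, but it has no bearing on the trial's main conclusions.

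**What to change.** In SAP 2.5.4.6, 3.5.4.6 and 4.5.4.5, change the upper limit of the middle band from 64 to 74. This restores the randomisation strata and introduces no data-driven choice.

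The Part A database was locked before 07 March 2023, and this SAP cites an eCRF dated 01 August 2023, so the correction should be made in a dated SAP update or recorded in the CSR. Any table already programmed or run with 60–64 should be rerun and the correction noted.

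The cost is one number in each of three sections, plus reruns if any such tables exist. Separately, the sponsor could state whether the Part A and Part B age summaries will be produced, as the protocol says, or only may be, as the SAP says.
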